## 7.3. Treatment Assignment

Group 1: ST266 dosed daily on Days 1-5, 8-12, 22, and 30 and then monthly for 7 months (Days 60, 90, 120, 150, 180, 210, and 240).

Group 2: ST266 dosed 2x/week (with at least one day between treatments) for the first 3 months and monthly for 5 months thereafter (Days 120, 150, 180, 210, and 240).

Group 3: Placebo dosed at the same frequency as Group 1.

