g Performed at each treatment visit, as well as at each evaluation visit.

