#### **9.5. Treatment Visits**

Treatment visits will consist of a review of the subject's medical and dental history, including recording concomitant medications. Additionally, the study medication will be applied to the buccal and lingual surfaces of the teeth. Following the application of the study medication an assessment of AEs will be performed. Subjects will be given oral hygiene instructions prior to the end of the visit.

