9. SAFETY EVALUATION

9.1 Overview of Safety Analysis Methods

Safety analyses will be presented descriptively on the safety population. No statistical testing will be performed.

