9.3 Adverse Events

The most recently available MedDRA dictionary version will be used for the classification of adverse events.

On-study AEs are those with a start date on or after the first treatment dose date and prior to the last treatment dose date + 30 Days.

On-study adverse events will be summarized overall by treatment group and by worst severity. Drug-related adverse events will also be tabulated.

All adverse events will be presented in a listing which includes first treatment dose date, onset and resolution date/day (or whether it is ongoing), system organ class and preferred term, investigator term, whether the event is serious, whether the adverse event involves

hematuria or proteinuria, severity grade, relationship to study drug, action taken, sequelae, and outcome.

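### Adverse events are asked about at every treatment visit and Group 2 has far more visits than placebo in Days 31-90, so the overall AE tables could be expected to show a modest Group 2 excess of mild, brief events with no drug effect

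*SAP*

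**What the plan says.** Protocol 7.3 sets two contact schedules. On one, "Group 1: ST266 dosed daily on Days 1-5, 8-12, 22, and 30 and then monthly for 7 months"; the placebo arm shares it ("Group 3: Placebo dosed at the same frequency as Group 1"). On the other, "Group 2: ST266 dosed 2x/week (with at least one day between treatments) for the first 3 months and monthly for 5 months thereafter". No arm receives placebo on the Group 2 schedule.

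The adverse event row of Protocol Table 3 carries a footnote: "Performed at each treatment visit, as well as at each evaluation visit". Protocol 9.5 repeats this for dosing visits: "Following the application of the study medication an assessment of AEs will be performed". Protocol 12.4.1.1 lists questioning, observation and unsolicited complaints as sources of AEs, and Protocol 12.1.4 has the oral mucosa examined at each visit.

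For analysis, SAP 9.3 states: "On-study adverse events will be summarized overall by treatment group and by worst severity". SAP 9.4 treats serious events and events leading to discontinuation in the same way. SAP 9.1 adds: "Safety analyses will be presented descriptively on the safety population. No statistical testing will be performed". Neither 9.3 nor 9.4 plans a table by period or at common visits, or mentions that contact frequency differs by arm. SAP 9.2 summarises the number of doses received but does not link it to the AE tables.

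**The concern.** When AEs are collected by asking, the number of times a subject is asked is part of the measurement. A mild event lasting a few days is more likely to be recorded if the next visit is 3 or 4 days away than if it is up to 30 days away. During most of the first three months that is the difference between Group 2 and placebo.

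Safety is a secondary objective, its endpoint is the frequency and pattern of AEs, and the study title includes evaluation of the treatment regimen. Because safety is purely descriptive, the arm-by-arm tables are the only planned basis for comparison. A Group 2 excess of mild events could be read as an effect of more frequent dosing when part or all of it is reporting. The vulnerable kind of event is also the kind to expect: Protocol 5.2 describes the 125 AEs and oral findings in the phase 1 study as all mild.

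**Working it through.** The documents state no visit totals or ratios, so there is no stated figure to reproduce.

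**Step 1. Contacts, from Protocol 7.3 and Table 3.**

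- Groups 1 and 3: 5 + 5 + 2 + 7 = 19 dosing days. The Day 15 and Day 270 evaluations are extra, giving 21 contacts. In Days 31-90 there are 2 (Days 60 and 90).
- Group 2: twice weekly for 12 to 13 weeks is 24 to 26 doses, plus 5 monthly doses, giving 29 to 31. Adding Day 270 gives 30 to 32 contacts if the other evaluations fall on dosing days, and about 34 to 36 if they do not. In Days 31-90: (60/7) × 2 ≈ 17 dosing visits.
- From Day 91 all arms share Days 120, 150, 180, 210, 240 and 270.

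The contact ratio is therefore about 17/2 = 8.5 in Days 31-90 and about 1.4 to 1.7 over the study.

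**Step 2. Time at risk.** SAP 9.3 counts events from the first dose up to 30 days after the last. The last planned dose is Day 240 in every arm, so planned time at risk is equal and a person-time rate would not remove the difference.

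**Step 3. Reporting model with no drug effect.** Assumptions: onset is uniform over Days 1-270 at the same rate in each arm, and the chance of reporting halves every h days between onset and the next visit. For a gap of L days between visits, the fraction reported is

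(1 − e^(−x))/x, with x = ln 2 × L/h.

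Days 31-90, with L = 30 on placebo and L = 3.5 on average in Group 2:

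| h (days) | Placebo | Group 2 | Ratio |
|---|---|---|---|
| 7 | 0.319 | 0.845 | 2.65 |
| 14 | 0.521 | 0.918 | 1.76 |
| 30 | 0.721 | 0.961 | 1.33 |

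**Step 4. The same model over the whole study, which is what SAP 9.3 tabulates.** The placebo gaps between contacts are eight of 1 day, two of 3 days, one of 7, one of 8 and eight of 30: 8 + 6 + 7 + 8 + 240 = 269 days. Group 2 has 89 days with gaps averaging 3.5 days, then six gaps of 30 days: 89 + 180 = 269. Multiplying each gap by its reported fraction and summing gives effective days observed:

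| h (days) | Placebo | Group 2 | Ratio |
|---|---|---|---|
| 7 | 100.0/269 = 0.372 | (75.2 + 57.5)/269 = 0.493 | 1.33 |
| 14 | 150.9/269 = 0.561 | (81.7 + 93.7)/269 = 0.652 | 1.16 |
| 30 | 200.6/269 = 0.746 | (85.5 + 129.8)/269 = 0.800 | 1.07 |

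Placing the doses on actual weekday patterns, with evaluations on dosing days or separate, gives 1.31 to 1.33, 1.15 to 1.16 and 1.07. The overall ratio is much smaller than the Days 31-90 ratio because 180 of the 269 days have identical schedules.

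**Step 5. Sensitivity.** With complete recall over 30 days the ratio is 1.0. Under a harsher rule, where an event is lost unless a visit falls within a fixed number of days of onset, the overall ratio is about 2.2 at 3 days, 1.56 at 7, 1.23 at 14 and 1.0 at 30.

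**Step 6. Early period.** In Days 1-12 Groups 1 and 3 have 10 dosing visits against about 4 in Group 2. The Step 3 model gives a Group 2 to placebo ratio of about 0.90 to 0.98 there, a reversal of at most about 10%, because Group 2's gaps are still only 3 to 4 days.

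**The case against.** The strongest reply is that the documents contain no recall or event-duration figure, so any excess is assumed. The protocol also works against loss between visits: medical and dental history and concomitant medications are updated at each visit, unsolicited complaints count, and events carry an onset date rather than needing to be present on the day. No formal inference is at stake. Serious events, discontinuations, severity and relatedness are tabulated separately, and an interested reader could rebuild a by-period comparison from the listing. Much of this stands. It limits the size of the effect and means that the tables could be expected to show an excess, not that they must. It does not remove the imbalance. Leaving the comparison to a listing also means it would be made after unblinding, and under SAP section 1 any added analysis would be labelled post hoc.

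A reader might infer more than the documents support in three ways:

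- **That the roughly eightfold visit ratio, or the 2.6-fold figure, describes the planned table.** Both belong to Days 31-90, which SAP 9.3 does not tabulate separately.
- **That the denser early visits on placebo could hide early reactions in Group 2.** The early reversal is too small to carry that.
- **That Group 2 should therefore be judged on Day 91 onward, or on events present at common visits.** Day 91 onward omits the twice-weekly phase, in which an effect of dosing frequency would arise, and a count on fixed days misses brief local reactions. Making either decisive could dismiss a real signal as reporting.

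**Conclusion.** The point holds in a limited form. The unequal contact schedule and the absence of any allowance for it in SAP 9.3 and 9.4 follow directly from the documents. The consequence is an expected, modest excess of mild, short-lived AEs on Group 2 in the overall table: about 1.3, 1.15 or 1.07 times placebo at assumed reporting half-lives of 7, 14 or 30 days, against about 2.6, 1.75 and 1.3 within Days 31-90. These figures rest on equal true rates, uniform onset and the assumed decline in reporting. Faster loss would raise them, and complete recall would bring them to 1.0. The comparison of Group 2 with Group 1 is affected in the same way. Group 1 versus placebo is not affected, because the schedules are identical, and serious events should be little affected because they are unlikely to be missed between visits. The change is worth making before database lock.

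**What to change.** In SAP 9.3, keep the overall table as planned and add two tables, both from onset and resolution dates already in the AE listing:

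- (a) On-study AEs by onset period (Days 1-12, 13-30, 31-90, 91 to end), by arm.
- (b) As a supportive table, the number of subjects with an AE ongoing at each common evaluation visit (Days 15, 30, 60, 90, 180 and 270), by arm.

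Add a sentence saying that contact frequency differs between Group 2 and the other arms, and that Group 2 versus placebo differences in non-serious AEs will be interpreted across all these tables in that light, with no one of them decisive.

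The cost is SAP wording and two tables, with no new data or visits. The limitation is that (b) misses events that start and resolve between common visits; the overall table and (a) still show those that were recorded.

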9.4 Deaths, Serious Adverse Events, and Other Significant Adverse Events

The number of deaths will be presented along with the corresponding reason for death.

On study serious adverse events will be classified by system organ class and preferred term. They will be presented overall by treatment group and by worst severity. Drug-related serious adverse events will also be tabulated.

On study adverse events leading to discontinuation will be classified by system organ class and preferred term. They will be presented overall by treatment group and by worst severity. Drug-related adverse events leading to discontinuation will also be tabulated.

9.5 Clinical Laboratory Evaluation

Blood is to be drawn and urine collected for laboratory analysis at Screening, and on Days 90 and 270. The following clinical laboratory parameters are to be assessed:

- Hematology: Complete blood count
- Blood chemistry: serum glucose, C-reactive protein, blood urea nitrogen, creatinine, electrolytes, HbA1c (at screening only), and liver function including bilirubin and hepatic enzymes
- Urinalysis: hematuria, proteinuria, pregnancy test (at screening and final visit only)

Tables will present continuous summary statistics for each lab parameter collected by visit and treatment group.

Laboratory values outside the normal range will be flagged as “high” or “low”. Percentage of subjects with values falling in high, normal, and low ranges will be summarized by lab parameter and visit, by treatment group.

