### **8.4. Subject Withdrawal Criteria**

Subjects may voluntarily withdraw from the study, or be removed from the study at the discretion of the investigator or sponsor at any time. If such withdrawal occurs, or if the subject fails to return for visits, the investigator should determine the primary reason for a subject's premature withdrawal from the study and record the reason in the subject's study records.

All subjects prematurely discontinuing from the trial, regardless of cause, should be scheduled as soon as possible for a follow-up safety visit, which will include all assessments planned for Day 270 (end of study).

For subjects who are lost to follow-up (i.e., those subjects whose status is unclear because they fail to appear for study visits without stating an intention to withdraw), the investigator should document all steps taken to contact the subject, e.g., dates of telephone calls, registered letters, etc.

Subjects who are withdrawn from the study after beginning treatment will not be replaced.

---

 For the purposes of subject exclusion, *diabetes* is defined as any subject with (i) a history of type 1 or type 2 diabetes, (ii) prior or concomitant prescription of diabetes medications, or (iii) a laboratory test for glycated hemoglobin  $\geq 6.5$ .

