#### **12.1.5. Laboratory Assessments**

Blood (10 to 15 mL) and urine samples (3 to 5 mL) will be sent to a certified laboratory for hematology, blood chemistry, and urine tests at screening and at Days 90 and 270. If a subject has any laboratory value that was normal upon entry into the trial and becomes abnormal, the sponsor's Medical Monitor will review the data with the investigator to assess whether the laboratory value represents a safety concern.

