#### **12.1.6. Hematology**

Complete blood count will be performed at screening and at Days 90 and 270. If a subject develops hemoglobin, hematocrit, or white blood cell count outside the normal range (as per the laboratory normal range values), that case will be reviewed by the sponsor's Medical Monitor. The Medical Monitor may determine that the subject will receive no further study drug treatment.

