#### **12.1.6.1. Blood Chemistry**

Serum glucose, C-reactive protein, blood urea nitrogen, creatinine, electrolytes, HbA1c (at screening only), and liver function including bilirubin and hepatic enzymes will be measured at screening and at Days 90 and 270.

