#### **12.1.6.2. Urinalysis**

Urinalysis will be performed at screening and at Days 90 and 270. If a subject develops hematuria or proteinuria after treatment is initiated, that case will be reviewed by the sponsor's Medical Monitor, who may determine that the subject will receive no further study drug treatment.

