##### 12.4.1.1. Methods of Collection

Adverse events may be collected as follows:

- Observing the participant

- Questioning the participant in an unbiased and non-leading manner
- Receiving an unsolicited complaint from the participant

An abnormal value or result from a clinical or laboratory evaluation can also indicate an AE if it is determined by the investigator to be clinically significant. If this is the case, it must be recorded in the source document and as an AE on the appropriate AE form(s). The evaluation that produced the value or result should be repeated until that value or result returns to normal or is stable, establishing a new baseline and the participant's safety is not at risk.

An abnormal laboratory value recorded at screening is not considered an AE, but is treated as a preexisting condition and should be recorded in the subject's medical history.

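### SAP 9.5 laboratory tables give prevalence by visit and arm but cannot count new-onset abnormalities; a by-arm shift table would (minor, cheap improvement)

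*SAP*

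**What the plan says.** SAP 9.5 names three draws (screening, Day 90, Day 270) and two kinds of output. One is continuous summary statistics for each parameter by visit and arm. The other is categorical: "Percentage of subjects with values falling in high, normal, and low ranges will be summarized by lab parameter and visit, by treatment group". It names no change from screening, no shift table, no new-onset count and no laboratory listing. No other SAP section fills the gap: the change-from-baseline summaries in SAP 8.3.3 are for efficacy endpoints. Vital signs, by contrast, get change from baseline and a listing (SAP 9.6.1).

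The protocol frames laboratory safety within the subject:

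- 12.1.5 sets the condition for review as "If a subject has any laboratory value that was normal upon entry into the trial and becomes abnormal".
- 12.1.6: "If a subject develops hemoglobin, hematocrit, or white blood cell count outside the normal range". The case then goes to the Medical Monitor, who may stop dosing.
- 12.1.6.2: "If a subject develops hematuria or proteinuria after treatment is initiated, that case will be reviewed", again with possible loss of further dosing.

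On recording, Protocol 12.4.1.1 says that an abnormal result "can also indicate an AE if it is determined by the investigator to be clinically significant", and treats a value already abnormal at screening as pre-existing. SAP 9.3 tabulates on-study AEs by arm. It counts those starting on or after the first dose and before the last dose date plus 30 days. Its AE listing carries an indicator for hematuria or proteinuria.

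**The concern.** A percentage at each visit shows how many subjects are out of range at that time. It does not show whether they are the subjects who were out of range at screening. The protocol's triggers are about becoming abnormal, and the planned tables cannot give that count by arm. Case review by the Medical Monitor deals with subjects one at a time and produces no by-arm tabulation.

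Hematuria and proteinuria have a further problem. Neither continuous statistics nor high/normal/low categories suit a present/absent finding. SAP 3 allows frequencies where appropriate, but no planned laboratory table conditions on absence at screening.

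At stake is a descriptive safety statement: how many subjects per arm developed a new laboratory abnormality. For a topical biologic given over eight months, a reader of the study report would reasonably look for that number.

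**Working it through.** The point concerns table content, so there is no figure in the plan to reproduce. The documents give 50 subjects per arm and expected dropout of about 10% (SAP 2.6) or 20% (Protocol 7.2). They give no rate of abnormality at screening, so every rate and count below is an assumption.

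**1. Margins do not fix the new-onset count.** Take the same N subjects at both visits, s abnormal at screening and d at Day 90. The number of new cases lies between max(0, d − s) and min(d, N − s). With N = 50, s = 8, d = 8, that is 0 to 8 new cases among 50 − 8 = 42 initially normal subjects, or 0% to 8/42 = 19.0%. The planned table shows 16% and 16% in either case.

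These bounds need the same subjects at both visits. SAP 3 bases percentages on subjects with data, and 10% to 20% dropout removes 5 to 10 of 50 per arm by Day 270. The bounds therefore do not carry over directly to the planned table, where changes in who is measured also enter.

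**2. Between arms, most of an excess survives if conditions match.** Let p0 be screening prevalence, b the share of abnormal subjects who normalise, and n the onset rate among initially normal subjects. Day 90 prevalence is d = p0(1 − b) + (1 − p0)n. Assume n = 10% against 2% (a true gap of 8 points) and b = 0.5 in both arms:

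| p0 | Higher-onset arm | Lower-onset arm | Gap |
|---|---|---|---|
| 15% | 0.075 + 0.085 = 16.0% | 0.075 + 0.017 = 9.2% | 6.8 points |
| 5% | 0.025 + 0.095 = 12.0% | 0.025 + 0.019 = 4.4% | 7.6 points |

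The gap equals (1 − p0) × 8 points, so 85% or 95% of it is kept. The value of b drops out only if it is the same in both arms. If the arms differ, the gap shifts by −p0 times the difference in b. For example, at p0 = 15% with b = 0.7 in the higher-onset arm and 0.3 in the other, it is 6.8 − 0.15 × 40 = 0.8 points.

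**3. Within an arm, onset is not identified.** The bounds on n are max(0, d − p0)/(1 − p0) to min(d, 1 − p0)/(1 − p0):

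| p0 | Day 90 prevalence | Onset rates that fit | Assumed truth |
|---|---|---|---|
| 15% | 16.0% | 1.2% to 18.8% | 10% |
| 15% | 9.2% | 0% to 10.8% | 2% |
| 5% | 12.0% | 7.4% to 12.6% | 10% |
| 5% | 4.4% | 0% to 4.6% | 2% |

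The gain from a shift table is therefore greatest for parameters often abnormal at screening.

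**4. Two post-baseline visits.** If all 50 are normal at screening, 5 abnormal at Day 90 and 5 at Day 270 means between max(5, 5) = 5 (10%) and 5 + 5 = 10 (20%) subjects ever abnormal.

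**5. The AE route at the last draw.** The last dose is nominally Day 240, and 240 + 30 = 270. SAP 9.3 requires onset before that date, so an AE dated to the nominal Day 270 draw is outside the on-study tables and appears only in the listing. With windows of ±7 days on both visits, the interval from last dose to last draw runs from 263 − 247 = 16 to 277 − 233 = 44 days. Some such events will therefore fall inside the window and others outside.

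**The case against.** The strongest reply is that no commitment is broken. The protocol clauses are rules for handling individual cases and do not promise a by-arm count. The safety endpoints are AEs and SAEs, safety output is descriptive without testing (SAP 9.1), and SAP 1 lets the study report add a table labelled post hoc. All of this stands and is why the point is minor. It does not make the margins able to supply the count, and prespecifying a table avoids the post-hoc label.

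Second, AEs already condition on screening: a value abnormal at entry is not an AE, and a pre-existing condition becomes one only if it worsens. This stands for values judged clinically significant. Other new out-of-range values get no by-arm new-onset count, and the AE tables are least reliable at the Day 270 draw.

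Third, the within-arm ranges are extremes. They need nearly all or nearly none of the screening abnormalities to persist. Eligibility also favours generally healthy subjects, which may keep screening prevalence low for many parameters. This is fair; at 5% prevalence the ranges are narrow.

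A reader might infer that the planned tables would hide a treatment-related excess, or that new abnormalities would go unexamined. The documents do not support either. The arms are randomised, the table includes screening so an imbalance there would show, most of a between-arm gap survives under matching rates, and the protocol sends individual cases for medical review.

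**Conclusion.** The point holds as a minor, inexpensive improvement to descriptive safety reporting. SAP 9.5 describes prevalence correctly but leaves new onset within each arm uncounted, and AE recording covers that only in part. Between-arm prevalence differences remain largely informative provided screening rates and normalisation rates match across arms. The sizes shown rest on assumed rates and counts and on the same subjects being measured at both visits. No endpoint, alpha level or efficacy conclusion is affected.

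**What to change.** In SAP 9.5 add, by treatment group on the safety population:

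- A shift table of screening category against worst post-baseline category for each parameter measured after screening, with high and low shown separately where both directions apply. This leaves out HbA1c, which is measured only at screening, and the pregnancy test.
- n/N and percent newly abnormal among subjects normal at screening who have at least one post-baseline value. Include values from the early-withdrawal visit, at which Protocol 8.4 schedules the Day 270 assessments.
- Hematuria and proteinuria as present or absent, with new onset among subjects without them at screening.
- A listing of repeat tests. Protocol 12.4.1.1 provides that "The evaluation that produced the value or result should be repeated until that value or result returns to normal or is stable", so the listing would show which new abnormalities were transient.

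All the values are already collected, so the cost is SAP wording and programming. The downside is extra table length across all laboratory parameters.
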